#### 5.5.1.2 As Treated (AT) Analysis

Data from all Device group subjects in the AT population will be analyzed similar to the primary analysis. For subjects who undergo other intervention for HF (e.g. MV surgery, LVAD implant or heart transplant), their follow-up information after the first intervention for HF will be excluded from the AT analysis if they have not experienced safety events prior to the date of the intervention.

#### 5.5.1.3 Per Protocol (PP) Analysis

Data from all Device group subjects in the PP population will be analyzed similar to the primary analysis. For subjects who undergo other intervention for HF (e.g. MV surgery, CRT implant), their follow-up information after the first intervention for HF will be excluded from the PP analysis if they have not experienced safety events prior to the date of the intervention.

#### 5.5.1.4 Tipping-point Analysis

Tipping point analysis on the primary safety endpoint at 12 months will be conducted as a sensitivity analysis. Subjects in the Safety Analysis population who withdraw from the study before completing a year of follow-up will be analyzed one at a time as having experienced a primary safety endpoint event on the date of withdrawal. In addition, patients with unevaluable echocardiograms at last follow-up will be analyzed one at a time as having experienced a primary safety endpoint event on the date that follow-up occurred.

#### 5.5.1.5 Subgroup Analyses for Primary Safety Endpoint

#### **5.5.1.5.1** Sex (male vs. female)

Subgroup analyses of sex will be performed. Major baseline and clinical characteristics will be summarized by sex.

A Kaplan-Meier analysis with stratification for sex will be performed for time to first event. Freedom from the safety composite at 12 months will be reported for the strata. An additional analysis will also be performed utilizing a Cox regression model for analyzing time to first event. The test for the sex effect will be performed at the 5% level of significance.

#### 5.5.1.5.2 Etiology of Cardiomyopathy (ischemic vs. non-ischemic)

Subgroup analyses of cardiomyopathy etiology will be performed. Major baseline characteristics will be summarized by etiology of cardiomyopathy.

A Kaplan-Meier analysis with stratification for cardiomyopathy etiology will be performed for time to first event. Freedom from the safety composite at 12 months will be reported for the strata. An additional analysis will also be performed utilizing a Cox regression model for analyzing time to first event. The test for the effect of etiology of cardiomyopathy will be performed at the 5% level of significance.

#### 5.5.1.5.3 Left Ventricular Ejection Fraction (LVEF > 40% vs. LVEF $\leq 40\%$ )

Subgroup analyses of Central Echocardiography Core Laboratory assessed baseline LVEF will be performed. Major baseline and clinical characteristics will be summarized by baseline LVEF.

A Kaplan-Meier analysis with stratification for LVEF will be performed for time to first event. Freedom from the safety composite at 12 months will be reported for the strata. An additional analysis will also be performed utilizing a Cox regression model for analyzing time to first event. The test for the LVEF effect will be performed at the 5% level of significance.

#### 5.5.1.5.4 Extreme Surgical Risk Status

Subgroup analyses of extreme surgical risk status (as assessed by the Central Eligibility Committee) will be performed. Major baseline and clinical characteristics will be summarized by extreme surgical risk status.

A Kaplan-Meier analysis with stratification for extreme surgical risk status will be performed for time to first event. Freedom from the safety composite at 12 months will be reported for the strata. An additional analysis will also be performed utilizing a Cox regression model for analyzing time to first event. The test for the effect of extreme surgical risk status will be performed at the 5% level of significance.

#### 5.5.1.6 Analysis of Poolability of Study Sites

Analysis of the site effect will be performed. A Cox regression model will be utilized for analyzing the time to first event. The model will include the effects of site. The site effect will be tested at the 15% level of significance.

The study will involve up to 100 sites. It is likely that there will be wide variation in the number of subjects enrolled across sites (due to differences in site start-up times and differences in subject volumes enrolled at sites). If model convergence is not achieved, sites will be categorized into the categories described below. The model will then include the effects of site category. In addition, a descriptive summary of events will be provided by site.

Large: Sites with more than 10 subjects

- Medium Large: Sites that enroll between 6 and 10 subjects
- Medium: Sites that enroll between 3 and 5 subjects
- Small: Sites that enroll fewer than 3 subjects

#### 5.5.2 Secondary Safety Endpoints

#### 5.5.2.1 Composite 30-Day Secondary Safety Endpoint

A composite of all-cause death, stroke, MI, or non-elective (urgent or emergent) cardiovascular surgery for device related complications in the Safety Analysis Population at 30 days will be used as a secondary measure of safety. The analysis of the secondary safety endpoint is a one-group test against a performance goal for the proportion of subjects in the Safety Analysis Population free from the composite of secondary safety events at 30 days. The null and alternative hypotheses may be stated as:

$$H_0$$
:  $P_D(30) \le 0.80 \text{ vs.}$ 

$$H_1: P_D(30) > 0.80$$

where, PD(30) is the proportion of subjects free from composite of secondary safety events at 30 days in the Safety Analysis Population. This endpoint will be evaluated at the one-sided significance level of 5% with an exact test for a single proportion. The denominator of the proportion will exclude subjects in the Safety Analysis Population who terminated from the study prior to the lower window of the 30-Day visit (Day 27) without any site reported adverse events.

Components of the secondary composite safety endpoint will be summarized and reported for the Device group.

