8.1 Definition of Adverse Event and Serious Adverse Event

8.1.1 Adverse Event (AE)

An adverse event is any untoward medical occurrence, unintended disease or injury, or untoward clinical signs (including abnormal laboratory findings) in subjects, users, or other persons, whether or not related to the investigational medical device.

This definition includes events related to the investigational medical device or comparator and/or the procedures involved. For users or other persons, this definition is restricted to events related to the investigational medical device.

An AE can therefore be any unfavorable and unintended sign (including an abnormal laboratory finding), symptom, or disease temporally associated with the use of a medicinal (investigational) product, whether or not related to the medicinal (investigational) product. Device failure may constitute an adverse event if an undesirable experience occurs

Adverse events information will be collected throughout the trial. Adverse events will be recorded on the electronic case report forms by the Investigator or designee. Event description, date of onset, severity, duration, and relationship to device will be recorded on the appropriate electronic case report form. Adverse events will be monitored through the course of the trial. A list of adverse events, which may result from this procedure, is located below in **Table 3**.

Note: Unchanged, chronic conditions are not adverse events and should not be recorded on the eCRF Adverse Event form. Pre-existing conditions that have not worsened are not considered AEs.

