8.4.2 Serious Adverse Event Reporting to Sponsor and IRB/EC

The Investigator will monitor the occurrence of AEs for each subject during the course of the clinical trial/investigation and report as required by this protocol in section 8 per AE and SAE definitions. AEs need to be collected from the time of randomization for randomized subjects and from the initiation of the MitraClip procedure for roll-in subjects on the appropriate AE eCRF form. Additional information with regards to an AE should be updated within the AE eCRF.

A fax form will be made available to allow the investigator to report SAEs in the event the entry cannot be made in the eCRF system. This does not replace the eCRF reporting system. All information must still be entered in the eCRF system as soon as feasible.

The investigator should report all SAEs to the Sponsor as soon as possible but no later than 3 calendar days from the day study personnel became aware of the event or as per the investigative site's local requirements if the requirement is more stringent than those outlined. The date the site staff became aware that the event met the criteria of a serious adverse event must be recorded in the source document.

Serious adverse events that occurred in the user or persons other than the study subject should not be entered in the eCRF system, however need to be reported on the SAE Notification Form provided by Sponsor.

The Investigator will further report the SAE to the local IRB/EC according to the institution's IRB/EC reporting requirements.

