#### 2.2 Secondary Objectives

There are two secondary safety objectives:

- To demonstrate that freedom from death (all-cause), stroke, myocardial infarction (MI), and non-elective (i.e., urgent or emergent) cardiovascular surgery for device related complications at 30 days post-procedure in the Device group is greater than 80%
- To demonstrate that the hazard ratio of all-cause mortality at 12 months between the Device and Control groups is less than 1.5

There are several secondary effectiveness objectives as described in the COAPT Protocol Version 8.0 Section 3.2.

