## 5.4.4 Safety Analysis (SA) Population

The Safety Analysis population is defined to consist of randomized Device group subjects in whom a MitraClip procedure is attempted.

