#### **5.8.3** Secondary Safety Endpoints

#### 5.8.3.1 Composite 30-Day Secondary Safety Endpoint

**Table 2** lists the event rates assumed for the components of the composite secondary safety endpoint in the Device group.

Tuble 2. Hisbumptions for Secondary Surety Event Rates at 20 Buys		
Event	Device Group	
Death	5%	
Stroke	2%	
MI	2%	
Non-elective CV Surgery for	3%	
Device Related Complications		
Total	12%	

Table 2: Assumptions for Secondary Safety Event Rates at 30 Days

Two thousand (2000) simulations were performed. A total of 305 subjects in the Device group (without attrition) provides > 95% power to reject the null hypothesis at the one-sided significance level of 5%.

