The number and proportion of subjects with the events through 12-month follow-up will be summarized by the binary method for both Device and Control groups. Subjects lost to follow-up or withdrawal before a time point (e.g. the 12-month visit) will be excluded from the summary unless they are known to have experienced the event prior to that time point (e.g. within 12 months).

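### The 30-day safety proportion keeps a subject who leaves before Day 27 after an adverse event of any kind, on the natural reading as free of the composite; the effect is small and one phrase corrects it

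*SAP*

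**What the plan says.** SAP 5.5.2.1 tests whether more than 80% of the Safety Analysis population is free of the composite at 30 days. The components are all-cause death, stroke, MI and non-elective cardiovascular surgery for device complications. On the method it says: "This endpoint will be evaluated at the one-sided significance level of 5% with an exact test for a single proportion". SAP 5.4.4 defines the population as "randomized Device group subjects in whom a MitraClip procedure is attempted".

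The only rule for incomplete follow-up removes from the denominator subjects who "terminated from the study prior to the lower window of the 30-Day visit (Day 27) without any site reported adverse events". Protocol 7.3.1 has no missing-data rule for this endpoint.

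Two protocol sections show how wide that condition is. Section 8.1.1: "An adverse event is any untoward medical occurrence, unintended disease or injury, or untoward clinical signs (including abnormal laboratory findings) in subjects". Section 8.4.2: "AEs need to be collected from the time of randomization for randomized subjects", that is, from before the procedure.

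SAP Appendix A.1, for the 12-month binary outcomes reported to CMS, conditions on the outcome itself. Subjects who leave early "will be excluded from the summary unless they are known to have experienced the event prior to that time point".

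**The concern.** Whether a subject had some adverse event says little about whether a component event followed after the subject left. Take two subjects who withdraw on day 8 with no component event. One had nausea, which Protocol Appendix F lists at 10% or more; the other had no adverse event. The second is excluded. The first stays in the denominator and, with no imputation or censoring rule, enters the numerator as free, although days 9 to 30 were not observed.

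The authors may have meant to retain subjects who died or had a component event before leaving. The text goes further than that. On the natural reading, the difference from an event-specific rule can only help the device, in a safety test that can support a labeling claim.

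**Working it through.** **Inputs.** Goal 80%, exact test, one-sided 5% (SAP 5.5.2.1). Assumed composite event rate 12%, so 88% free, and N = 305 without attrition (SAP 5.8.3.1, Table 2). Attrition 7.5% at 12 months comes from the primary sample-size assumptions (SAP 5.8.1, 5.8.2). The documents do not give k, the number of early terminators kept because of a non-component adverse event.

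**Step 1: the plan's own figure.** The smallest r with P(Bin(305, 0.80) ≥ r) ≤ 0.05 is r = 256, which is 256/305 = 83.9%. Its exact size is 0.0471. Power at 88% is P(Bin(305, 0.88) ≥ 256) = 0.986. This agrees with the SAP's statement: "A total of 305 subjects in the Device group (without attrition) provides > 95% power to reject the null hypothesis".

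**Step 2: how many subjects.** With attrition spread evenly, 305 × 0.075 × 27/365 = 1.7. A constant withdrawal rate gives 305 × (1 − 0.925^(27/365)) = 1.75. Either figure is a ceiling on k at that attrition rate, because leavers with no adverse event are excluded.

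**Step 3: the rule as written, each kept leaver a certain success.** Size = P(Bin(305 − k, 0.80) ≥ 256 − k). Estimate at a true 88% = (0.88 × (305 − k) + k)/305.

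| k | Size at true 80% | Estimate at true 88% |
|---|---|---|
| 0 | 0.0471 | 88.00% |
| 1 | 0.0498 | 88.04% |
| 2 | 0.0527 | 88.08% |
| 3 | 0.0557 | 88.12% |
| 5 | 0.0622 | 88.20% |

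Averaging the size over k distributed as Poisson with mean 1.7 gives 0.0520. Under that distribution P(k ≥ 5) is about 3%, so the last row is unlikely at the planned attrition.

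**Step 4: relaxing certain success.** Component events before leaving still count as failures. Suppose k = 2 and each leaver has a 90% chance of being recorded free (an assumption). Size = 0.81 × 0.0527 + 0.18 × 0.0383 + 0.01 × 0.0272 = 0.0499. The three tail probabilities are P(Bin(303, 0.80) ≥ 254), P(≥ 255) and P(≥ 256).

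**Step 5: excluding these subjects.** The cut-off is recomputed for the smaller n, and the remaining subjects are assumed to keep the same true rate.

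| k | n | Cut-off | Size | Power at 88% |
|---|---|---|---|---|
| 1 | 304 | 255 | 0.0498 | 0.987 |
| 2 | 303 | 255 | 0.0383 | 0.981 |
| 5 | 300 | 252 | 0.0457 | 0.984 |

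**The case against.** The strongest reply is that the SAP says who leaves the denominator but not how a retained early leaver enters the numerator. If the numerator meant subjects known to be free at 30 days, retention would lower the estimate: 0.88 × 303/305 = 87.4% for two such subjects. So a reader might infer that the rule can only raise observed freedom, but the documents do not establish this. It holds on the natural reading, in which a subject with no recorded component event is free.

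The affected group is also narrow. Protocol 6.16.1 requires two consecutive missed visits before a subject is lost to follow-up. After discharge only the 1-week contact falls due before Day 27, and the 30-day window stays open to Day 44 (Protocol Table 1), so loss to follow-up can hardly be declared by then. Death is itself a component event. What remains is mainly voluntary withdrawal, which Protocol 10.14.6 says requires discussion with the sponsor. A reader might also infer that most early leavers would be turned into successes. Broad adverse-event collection makes that plausible, but the documents give no any-event rate for them.

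Finally, Appendix A.1 is not a neutral standard. It governs 12-month two-group summaries, and keeping leavers with events while dropping those without is slightly conservative. It shows only that the SAP uses an event-specific condition elsewhere.

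These points limit the size of the concern. They do not justify making exclusion depend on an unrelated adverse event.

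**Conclusion.** The point holds as a minor wording defect. As written, an early terminator with an unrelated adverse event and no component event stays in the denominator and, with no other handling stated, counts as free.

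It would be tempting to say that this breaks the one-sided 5% level. The figures do not support that at the planned attrition. The size is just under 5% with one such subject or with two at a 90% chance of being recorded free, 5.3% with two certain successes, and about 5.2% on average under certain success. Larger excesses need more early leavers than the planning assumption implies. The estimate at 88% moves by about 0.1 point.

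Consequence is limited further by position. In SAP 5.9 this endpoint comes last of ten sequential tests, reached only after both primary endpoints and the nine preceding secondary tests are met. The planned 88% is also about four points above the 83.9% cut-off. The rule matters only for a result near the goal. These conclusions rest on 7.5% yearly attrition spread evenly, 305 subjects in the Safety Analysis population, and the natural reading of the numerator.

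**What to change.** In SAP 5.5.2.1, replace the adverse-event condition at the end of the exclusion sentence with: *without a component event of the composite (death, stroke, MI, or non-elective cardiovascular surgery for a device related complication)*. That matches the logic of Appendix A.1 and settles the numerator, because every early terminator who remains has had a component event.

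Add one sensitivity analysis that counts all event-free early terminators as failures. With the 256 cut-off its power at 88% is 0.972 for two such subjects and 0.931 for five.

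The cost is one phrase and one line of output. The observed freedom may be very slightly lower, and power of the main test at 88% stays at about 98%. No change to design or sample size is needed. Priority: nice to have.

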#### 5.5.2.2 All-Cause Mortality at 12 Months

The hazard ratio of all-cause mortality from the time of randomization to 12 months between the Device and Control groups is a secondary measure of safety. The null and alternative hypotheses are stated as:

**H**0: HR 
$$\geq$$
 1.5 vs.

$$H_1$$
: HR < 1.5

where, HR is the hazard ratio of all-cause mortality at 12 months between the Device and Control groups.

Follow-up will be truncated at 12 months. A Cox regression model with only treatment effect as covariate will be used to estimate the hazard ratio. The one-sided 95% upper confidence bound for the HR will be calculated as HR +  $Z_{\alpha}$  × SE estimation from the Cox regression model, where  $Z_{\alpha}$  = 100(1- $\alpha$ )th percentile of the standard normal distribution. The null hypothesis will be rejected at the one-sided significance level of 5% if the one-sided 95% upper confidence bound for HR is less than 1.5.

If non-inferiority of Device group to Control group is demonstrated, the estimated HR is lower than 1, and the difference in the survival curves between Device group and Control group is maintained or increases after 12 months, then a superiority test of all-cause mortality will be performed in the pre-specified fixed sequential testing for all secondary effectiveness endpoints (See **Section 5.9 Multiplicity Adjustments**). All available follow-up through 24 months at the time of data cut-off will be included in the analysis. The null and alternative hypotheses for superiority test are stated as:

 $H_0$ : HR = 1.0 vs.

**H**1: HR  $\neq$  1.0

The superiority null hypothesis will be rejected at the two-sided significance level of 5% if the 95% upper confidence bound for HR is less than 1.

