## **Hypothesis:**

The null and alternative hypotheses are stated as:

 $H_0$ : RRR = 0 vs.

 $\mathbf{H_1}$ : RRR  $\neq 0$ 

where RRR is the relative risk reduction in the rate of recurrent hospitalization due to treatment with the MitraClip device. All hospitalizations will be included as events in the analysis.

The Joint Frailty Model method will be used to model the recurrent hospitalization data and estimate the RRR.

RRR = (1- Hazard Ratio of Device vs. Control) =  $(1 - e^{\beta})$  where  $\beta$  is the regression coefficient of the recurrent hospitalization in the JFM model.

This endpoint will be analyzed when the last subject completes 12 months of follow-up. All available follow-up through 24 months at the time of data cut-off will be included in the analysis. Subjects who do not experience any hospitalizations will be censored on their data cut-off date. Subjects who die will be censored on the date of death. Subjects who withdraw from the trial without a hospitalization will be censored on the date of withdrawal.

The null hypothesis is rejected if the regression coefficient for the Device group is significant at the two-sided significance level of 5%. The two-sided 95% confidence interval is calculated as RRR  $\pm$   $Z_{\alpha/2} \times$  SE where RRR and SE are estimated from the Joint Frailty Model and  $Z_{\alpha/2} = 100(1-\alpha/2)$ th percentile of the standard normal distribution. Beneficial treatment effect is established if the lower two-sided 95% confidence bound of the relative risk reduction is greater than zero.

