#### 5.8.3.2 All-Cause Mortality at 12 Months

Two thousand (2000) simulations were performed. Assuming 27% mortality in the Control group, 22% mortality in the Device group, and 7.5% attrition in both groups at 12 months, a total of 610 subjects will provide > 90% power to reject the null hypothesis at the one-sided significance level of 5%.

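### The mortality non-inferiority bound is written as HR + Z × SE instead of on the log scale; taken literally, the stated one-sided 5% error becomes about 7.0% or 11.6%, depending on the SE meant

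*SAP*

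**What the plan says.** SAP 5.5.2.2 tests H0: HR ≥ 1.5 for all-cause mortality, with follow-up truncated at 12 months. On the model it says: "A Cox regression model with only treatment effect as covariate will be used to estimate the hazard ratio". On the bound it says: "The one-sided 95% upper confidence bound for the HR will be calculated as HR", followed by + Z × SE, with the SE described only as coming from the Cox regression. The null hypothesis is to be "rejected at the one-sided significance level of 5% if the one-sided 95% upper confidence bound for HR is less than 1.5".

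Protocol 7.3.2 asks for the 95% upper bound to lie below 1.5 but gives no formula. Nothing else in either document puts this bound on the log scale.

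Two related wordings:
- The superiority null hypothesis in the same SAP section is "rejected at the two-sided significance level of 5% if the 95% upper confidence bound for HR is less than 1".
- For all-cause recurrent hospitalization, SAP 5.6.2.7 says: "The two-sided 95% confidence interval is calculated as RRR", followed by ± Z × SE. The same paragraph rejects on the significance of the regression coefficient.

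SAP 5.9 places the mortality non-inferiority test second of ten in the fixed sequence of secondary tests.

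**The concern.** A Cox model returns beta = log HR and SE(beta), and beta is the quantity that is approximately normal. The usual limit for the HR is therefore exp(beta + Z × SE(beta)). The SAP instead adds Z × SE to the HR itself. It leaves open whether the SE is the delta-method SE of the HR, which is HR × SE(beta), or the SE of log HR that Cox output reports directly. Under either literal reading the bound falls below the log-scale bound in the region that decides the test, so non-inferiority is declared too easily.

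At stake are the error level of a safety claim on mortality and, through the fixed sequence, access to the eight tests that follow. One dataset could also support opposite conclusions depending on how a programmer reads one line.

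**Working it through.** **Inputs.** SAP 5.8.3.2: "Assuming 27% mortality in the Control group, 22% mortality in the Device group, and 7.5% attrition in both groups at 12 months", 610 subjects, power stated as >90%. Allocation is 1:1 (SAP 5.1), so n = 305 per arm. The margin is 1.5, one-sided 5%, z = 1.645 (SAP 5.5.2.2). Exponential death and attrition times are an assumption; the SAP gives no time pattern for this calculation.

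**Formulas.**
- Hazards: control h = −ln(0.73) = 0.3147; attrition c = −ln(0.925) = 0.0780; device hazard = HR × h.
- Expected deaths per arm over 12 months: n × h/(h + c) × (1 − exp(−(h + c))).
- SE(log HR) = sqrt(1/d_control + 1/d_device), written s below.

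**The three rules.** Non-inferiority is declared if the observed HR is below:
- log scale: 1.5 × exp(−1.645 s)
- as written, SE of the HR: 1.5 / (1 + 1.645 s)
- as written, SE of log HR: 1.5 − 1.645 s

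**The SAP's own power figure first.** Planned HR = ln(0.78)/ln(0.73) = 0.789. Expected deaths are 79.4 + 64.7 = 144.0 before rounding, and s = 0.1675. Log-scale power = Phi((ln 1.5 − 1.645 × 0.1675 − ln 0.789)/0.1675) = 98.6% (simulated 98.5%), which is consistent with >90%. The two additive readings give 99.1% and 99.6%.

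**Type I error at a true HR of 1.5.** Deaths: control 79.4, device 110.7, total 190.1. s = sqrt(1/79.4 + 1/110.7) = 0.1471. The probability of passing is Phi(ln(limit/1.5)/s).

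| Rule | Largest HR that passes | Type I error | Cox simulation (two sets of 40,000 runs) |
|---|---|---|---|
| Log scale | 1.178 | 5.0% | 5.1%, 5.1% |
| As written, SE of the HR | 1.208 | 7.0% | 7.1%, 7.3% |
| As written, SE of log HR | 1.258 | 11.6% | 11.5%, 11.9% |

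**Sensitivity.** With 7.5% attrition and control mortality varied from 15% to 35%, the two additive readings give 7.7% down to 6.8%, and 10.9% up to 11.8%.

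**Where conclusions differ.** When the event count is matched to the observed HR instead of to a true HR of 1.5, the limits are 1.165, 1.198 and 1.250. For example, an observed HR of 1.19 corresponds to about 171 deaths (79.4 + 91.9) and s = 0.1532:
- log scale: 1.19 × exp(1.645 × 0.1532) = 1.531, fails
- SE of the HR: 1.19 × (1 + 1.645 × 0.1532) = 1.490, passes
- SE of log HR: 1.19 + 1.645 × 0.1532 = 1.442, passes

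**The related wordings.** For RRR, write x = 1.96 × SE(beta). The log-scale rule for benefit is HR < exp(−x). With the SE of the HR, the additive rule is HR < 1/(1 + x), which is looser, so the coefficient test in the same paragraph governs. With SE(beta), it is HR < 1 − x, which is stricter. Neither reading inflates the error. The superiority rule already states a two-sided 5% level and only fails to name the limit.

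**The case against.** The strongest reply is that the formula is shorthand. The section fixes a one-sided 5% level and names a 95% upper bound from a Cox model, and the usual exponentiated limit satisfies both. The authors work on the log scale elsewhere: RRR is defined as 1 − e^β in SAP 5.6.1 and 5.6.2.7, and SAP 5.8.2 estimates the logarithm of 1 − RRR. If that is what was meant, the error stays near 5%. This is plausible. But the SAP gives an explicit calculation, uses the additive form again in 5.6.2.7, and nowhere says that an exponentiated limit is intended.

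The two figures also do not have equal standing. The 7.0% reading is a Wald interval on the HR scale. It is valid asymptotically, and its excess reflects a poor choice of scale at about 190 deaths. The 11.6% reading adds a log-scale SE to a ratio and is best seen as the worst case. Both points are fair, but neither reading holds the level that the SAP states.

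The practical reach is narrow:
- The rules disagree only for observed HRs of about 1.16 to 1.25, against a planned 0.79. At that planned HR they disagree in about 1% of trials or fewer (98.6% against 99.1% or 99.6%). If the true HR is 1.0, disagreement rises to about 4% or 9%.
- The superiority test requires an estimated HR below 1. Even at an HR of 1.0 (79.4 deaths per arm, s = 0.159) the log-scale bound is exp(1.645 × 0.159) = 1.30, so access to that test is unaffected.
- Secondary tests run only if both primary endpoints are met, and the next test in sequence ranks death first.

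These points limit the importance; they do not make the formula right. The RRR and superiority items are editorial.

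**Conclusion.** The concern holds. The formula in SAP 5.5.2.2, applied as written, does not deliver the one-sided 5% level stated in the same paragraph: about 7.0% with the SE of the HR, and about 11.6% with the SE of log HR. These figures rest on 305 per arm, 27% control mortality, 7.5% attrition, proportional hazards and exponential times. The excess over 5% persists across control mortality from 15% to 35%. If the formula is only shorthand for the exponentiated limit, there is no excess, but the SAP has to say so.

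This should be fixed, but it does not threaten the trial. Under SAP 5.10 success rests on the two primary endpoints, and the stated >90% power for this test is not in question.

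**What to change.** In SAP 5.5.2.2, replace the formula with: upper bound = exp(beta + 1.645 × SE(beta)), where beta and SE(beta) are the log hazard ratio and its standard error from the Cox model.

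Two clarifications for consistency, with no effect on error rates claimed:
- In SAP 5.5.2.2, name the superiority limit as the upper limit of the two-sided 95% interval, exp(beta + 1.96 × SE(beta)).
- In SAP 5.6.2.7, write the interval as 1 − exp(beta ± 1.96 × SE(beta)), so that it agrees with the coefficient test.

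The cost is one formula correction and two wording edits. Data collection, sample size and patients are unaffected, and power for the non-inferiority test remains about 98.5%.
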